1.2. Schema

Part 1:

[figure not shown]
Abbreviations: PBO = placebo.

Part 2:

Abbreviations: PBO = placebo.

PART 3:

1.3. Schedule of Activities (SoA)

Screening procedures may be conducted over more than 1 day, as long as all activities are completed within the allowed interval tolerance. Screening and Day 1 procedures may occur on the same day.

Participants who test positive for SARS-CoV-2 during the Evaluation Period may have their scheduled visit(s) conducted as a remote health assessment. Refer to the study day and visit type table in Section 4.1.2 for additional clarification.

Early Termination Visits are conducted when the participant is withdrawn from the study prior to the post-evaluation follow-up.

1.3.1. Part 1 and Prevention Cohort of Part 2

Procedures	Screening	Evaluation Period										ETV	Post-Evaluation Follow-Up			Comments
		1	2-7	8	15	22	29	36	43	50	57		85	141	169	
Study Day	Max 7-day window	1	2-7	8	15	22	29	36	43	50	57		85	141	169	
Visit window (\pm number of days)	--	--	--	2	2	2	2	2	2	2	2		7	7	7	
Randomization		X														
Administer study intervention (IV infusion)		X														
Informed Consent	X															
Inclusion and exclusion criteria review	X															
Demographics	X															Including age, gender, race, ethnicity
Preexisting conditions and medical history	X															Obtained from interview or available information. For participants with symptoms suggestive of COVID-19, obtain timing of onset of symptoms

Procedures	Screening	Evaluation Period										ETV	Post-Evaluation Follow-Up			Comments
Study Day	Max 7-day window	1	2-7	8	15	22	29	36	43	50	57		85	141	169	
Visit window (\pm number of days)	--	--	--	2	2	2	2	2	2	2	2		7	7	7	
Prior treatments of special interest	X															Within the last 2 weeks: NSAIDs, antivirals, antibiotics, anti-malarials, corticosteroids, immunomodulators, or other investigational treatments. At any time: SARS-CoV-2 vaccine
Tobacco use	X															Never/ former/ current use
Concomitant medications	X	X	X	X	X	X	X	X	X	X	X	X	X	X		
Adverse events (AEs)	X	X	X	X	X	X	X	X	X	X	X	X	X	X	X	Any events that occur after signing the informed consent are considered AEs as defined in Section 10.3, Appendix 3.
Physical examination	X															
Symptom-directed physical exam		X										X	X	X		As indicated based on participant status and standard of care.
Height	X															
Weight	X															
Vital signs	X	Daily										X	X	X		Documentation of hospital-based exam is acceptable. Includes: body temperature, pulse rate, BP, SpO ₂ , respiratory rate, FiO ₂ if known, and method of delivery, if applicable. Record while participant is at rest.

Procedures	Screening	Evaluation Period										ETV	Post-Evaluation Follow-Up			Comments
Study Day	Max 7-day window	1	2-7	8	15	22	29	36	43	50	57		85	141	169	
Visit window (\pm number of days)	--	--	--	2	2	2	2	2	2	2	2		7	7	7	
Hospitalization events		Daily										X	X	X		Record if the following events occur: 
Emergency room visitshospitalizedICU admittance,Extended care facility admittance,and discharge for any of the above
Clinical status and concomitant procedures of special interest in hospitalized participants		Daily										X	X	X		Documentation from hospital records is acceptable. Includes: consciousness status (ACVPU), limitation on activities due to COVID-19, and requirements for 
Ongoing hospital medical careSupplemental oxygennon-invasive ventilation or a high flow oxygen devicemechanical ventilationextracorporeal membrane oxygenation, oradditional organ support (e.g. pressors, renal replacement)
Clinical symptoms and interventions of interest		Daily										X	X			See Table 1 for clinical symptoms and interventions of interest.

Procedures	Screening	Evaluation Period										ETV	Post-Evaluation Follow-Up			Comments
Study Day	Max 7-day window	1	2-7	8	15	22	29	36	43	50	57		85	141	169	
Visit window (\pm number of days)	--	--	--	2	2	2	2	2	2	2	2		7	7	7	
Symptoms Questionnaire	X	Daily										X	X		See Section 8.1.2.	
SARS-CoV-2 POC Test (Nasal Swab)	X														Applies to participants in Part 2 only. Result must be determined prior to collecting swabs for PCR test.	
SARS-CoV-2 Serology		X				X			X	X	X	X	X	X	Day 1: pre-dose. assessed at a central laboratory	
SARS-CoV-2 nasopharyngeal swab (for PCR test) taken from both nostrils		X													Day 1: pre-dose. assessed at a central laboratory	
SARS-CoV-2 nasal swab (for PCR test) taken from both nostrils		X		X	X	X	X	X	X	X	X	X	X		Day 1: pre-dose. assessed at a central laboratory No samples needed if participant is hospitalized.*	

Procedures	Screening	Evaluation Period										ETV	Post-Evaluation Follow-Up			Comments
Study Day	Max 7-day window	1	2-7	8	15	22	29	36	43	50	57		85	141	169	
Visit window (\pm number of days)	--	--	--	2	2	2	2	2	2	2	2		7	7	7	
Urine pregnancy	X	X										X		X		Only for WOCBP (Section 10.4, Appendix 4) Local laboratory. Test performed in the 24 hours prior to study entry will be accepted for determination of eligibility. No samples needed if participant is hospitalized.*
Hematology		X			X				X	X	X	X				Day 1: pre-dose. Assayed by Lilly-designated laboratory No samples needed if participant is hospitalized.*
Clinical Chemistry		X			X				X	X	X	X				Day 1: pre-dose. Assayed by Lilly-designated laboratory No samples needed if participant is hospitalized.*
LDH		X							X	X						Day 1: pre-dose. Assayed by Lilly-designated laboratory No samples needed if participant is hospitalized.*

Procedures	Screening	Evaluation Period										ETV	Post-Evaluation Follow-Up			Comments
Study Day	Max 7-day window	1	2-7	8	15	22	29	36	43	50	57		85	141	169	
Visit window (± number of days)	--	--	--	2	2	2	2	2	2	2	2		7	7	7	

 • C-reactive protein; high-sensitivity • Ferritin • D-dimer • Procalcitonin • Troponin 		X										X	X			Day 1: pre-dose. Assayed by Lilly-designated laboratory No samples needed if participant is hospitalized.*
PK sample		X					X					X	X	X	X	Day 1: pre-dose. For participants in Part 2, Day 1 collection is post-dose only (approx. 30 minutes after end of infusion). Assayed by Lilly-designated laboratory No samples needed if participant is hospitalized.*
Immunogenicity (ADA) sample		X					X					X	X	X	X	Day 1: pre-dose. Remaining days: Collect with time-matched PK sample. No samples needed if participant is hospitalized.*
Exploratory biomarker samples		X					X					X	X	X	X	Day 1: pre-dose Assayed by Lilly-designated laboratory No samples needed if participant is hospitalized.*
Pharmacogenetics sample		X														Assayed by Lilly-designated laboratory

Abbreviations: ACVPU = alert, confusion, voice, pain, unresponsive; ADA = antidrug antibody; AE = adverse event; BP = blood pressure; COVID-19 = coronavirus disease – 2019; FiO2 = fraction of inspired oxygen in the air; ETV = early termination visit; FiO2 = fraction of inspired oxygen; ICU = intensive care unit; IV = intravenous; LDH = lactate dehydrogenase; NSAID = nonsteroidal anti-inflammatory drug; PCR = polymerase chain reaction; PK = pharmacokinetic; POC = point of care; SpO2 = saturation of peripheral oxygen; SARS-CoV-2 = severe acute respiratory syndrome coronavirus 2; WOCBP = women of child-bearing potential

* Participants will continue to follow the Schedule of Activities upon discharge from hospital. No local lab result data will be collected in the eCRF while hospitalized.

1.3.2. Part 2 Treatment Cohort and Part 3

Screening for Part 2 is described in the table above (Section 1.3.1). Screening is provided below for reference.

Procedures	Screening	Evaluation Period			ETV	Post-treatment follow-up	Comments
Study Day	Max 7 day window	1	8	29		85	
Visit window (\pm number of days)	--	--	1	2		7	
Randomization		X					
Administer study intervention (IV infusion)		X					
Informed Consent	X						
Inclusion and exclusion criteria review	X						Note that eligibility criteria for Part 2 and Part 3 are different.
Demographics	X						Including age, gender, race, ethnicity
Preexisting conditions and medical history	X						Obtained from interview or available information. For participants with symptoms suggestive of COVID-19, obtain timing of onset of symptoms
Prior treatments of special interest	X						Within the last 2 weeks: NSAIDs, antivirals, antibiotics, anti-malarials, corticosteroids, immunomodulators, or other investigational treatments. At any time: SARS-CoV-2 vaccine
Tobacco use		X					Never/ former/ current use
Concomitant medications		X	X	X	X	X	
Adverse events (AEs)	X	X	X	X	X	X	Any events that occur after signing the informed consent are considered AEs as defined in Section 10.3, Appendix 3.
Physical examination	X						
Symptom-directed physical exam		X			X	X	As indicated based on participant status and standard of care.

Procedures	Screening	Evaluation Period			ETV	Post-treatment follow-up	Comments
Study Day	Max 7 day window	1	8	29		85	
Visit window (± number of days)	--	--	1	2		7	
Height		X					
Weight		X					
Vital signs	X	X	X	X	X	X	Documentation of hospital-based exam is acceptable. Includes: body temperature, pulse rate, BP, SpO ₂ , respiratory rate, FiO ₂ if known, and method of delivery, if applicable. Record while participant is at rest.
Hospitalization events		X	X	X	X	X	Record if the following events occur: 
Emergency room visitshospitalizedICU admittance,Extended care facility admittance,and discharge for any of the above
Clinical status and concomitant procedures of special interest in hospitalized participants		Daily		X	X		Documentation from hospital records is acceptable. Includes: consciousness status (ACVPU), limitation on activities due to COVID-19, and requirements for 
Ongoing hospital medical careSupplemental oxygennon-invasive ventilation or a high flow oxygen devicemechanical ventilationextracorporeal membrane oxygenation, oradditional organ support (e.g. pressors, renal replacement)
SARS-CoV-2 Serology		X		X	X	X	Day 1: pre-dose. assessed at a central laboratory
Documentation of positive SARS-CoV-2 viral infection	X						Applies to participants in Part 3 only. Sample for first positive test must be collected within 10 days prior to start of infusion. Local laboratory and/or Point-of-Care testing.

Procedures	Screening	Evaluation Period			ETV	Post-treatment follow-up	Comments
Study Day	Max 7 day window	1	8	29		85	
Visit window (\pm number of days)	--	--	1	2		7	
SARS-CoV-2 nasopharyngeal swab taken from both nostrils		X	X	X	X	X	Day 1: pre-dose. assessed at a central laboratory No samples needed if participant is hospitalized.*
Urine pregnancy	X	X			X	X	Only for WOCBP (Section 10.4, Appendix 4) Local laboratory. Test performed in the 24 hours prior to study entry will be accepted for determination of eligibility. No samples needed if participant is hospitalized.*
Hematology		X		X	X	X	Day 1: pre-dose. Assayed by Lilly-designated laboratory No samples needed if participant is hospitalized.*
Clinical Chemistry		X		X	X	X	Day 1: pre-dose. Assayed by Lilly-designated laboratory No samples needed if participant is hospitalized.*

 • C-reactive protein; high-sensitivity • Ferritin • D-dimer • Procalcitonin • Troponin 		X		X	X		Day 1: pre-dose. Assayed by Lilly-designated laboratory No samples needed if participant is hospitalized.*
PK sample		X		X	X	X	Day 1: post-dose only (approx. 30 minutes after end of infusion) Assayed by Lilly-designated laboratory No samples needed if participant is hospitalized.*
Immunogenicity (ADA) sample		X		X	X	X	Day 1: pre-dose. Remaining days: Collect with time-matched PK sample. No samples needed if participant is hospitalized.*

Procedures	Screening	Evaluation Period			ETV	Post-treatment follow-up	Comments
Study Day	Max 7 day window	1	8	29		85	
Visit window (± number of days)	--	--	1	2		7	
Exploratory biomarker samples		X		X	X	X	Day 1: pre-dose Assayed by Lilly-designated laboratory No samples needed if participant is hospitalized.*
Pharmacogenetics sample		X					Assayed by Lilly-designated laboratory

Abbreviations: ACVPU = alert, confusion, voice, pain, unresponsive; ADA = antidrug antibody; AE = adverse event; BP = blood pressure; COVID-19 = coronavirus disease – 2019; FiO2 = fraction of inspired oxygen in the air; ETV = early termination visit; FiO2 = fraction of inspired oxygen; ICU = intensive care unit; IV = intravenous; NSAID = nonsteroidal anti-inflammatory drug; PK = pharmacokinetic; SpO2 = saturation of peripheral oxygen; SARS-CoV-2 = severe acute respiratory syndrome coronavirus 2; WOCBP = women of child-bearing potential.

* Participants will continue to follow the Schedule of Activities upon discharge from hospital. No local lab result data will be collected in the eCRF while hospitalized.

2. Introduction

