This amendment will allow participants with COVID-19 to enroll in Part 3 (treatment only) of Study PYAD who have recovered from prior COVID-19 infection, or have received prior administration of convalescent plasma, monoclonal antibody, or vaccine for SARS-CoV-2. Inclusion will allow for collection of data to explore safety of treatment of LY3819253 alone or in combination with LY3832479 in any of these participant populations.

Section # and Name	Description of Change	Brief Rationale
Section 1.3.1 Part 1 and Prevention Cohort of Part 2	Updated “Prior treatments of special interest” to collect prior use of SARS-CoV-2 vaccine.	The SARS-CoV-2 vaccine is now allowed.
Section 1.3.2 Part 2 Treatment Cohort and Part 3		
2.2 Background	Added background on PYAB interim results.	Emerging data.
2.3 Benefit/Risk Assessment	Updated risk information for LY3819253.	Emerging data.
4.2 Scientific Rationale for Study Design	Added rationale for participants who have received the SARS-CoV-2 vaccine. Added language for Part 3 to reflect that participants who were in independent living situations at the facilities could be enrolled.	Vaccines are now available to the public and those who received a vaccine are allowed in the study. Clarification.
5.2 Exclusion Criteria	Updated Criteria 7, 8, 9, 11, 12, and 13.	This amendment will allow participants with COVID-19 to enroll in Part 3 (treatment only) of the study having recovered from prior COVID-19 infection, or having received prior administration of convalescent plasma, monoclonal antibody, or vaccine for COVID-19. Inclusion will allow for collection of data to explore safety of treatment of LY3819253 alone or in combination with LY3832479 in any of these participant populations.

Section # and Name	Description of Change	Brief Rationale
6.3 Measures to Minimize Bias: Randomization and Blinding	Added stratification factor for whether a participant received a vaccine or not prior to screening	The SARS-CoV-2 vaccine is now allowed
11 References	Added Chen et al. 2020 reference	Source for information in Section 2.3

Table of Contents

1. Protocol Summary	8
1.1. Synopsis	8
1.2. Schema	15
1.3. Schedule of Activities (SoA)	17
1.3.1. Part 1 and Prevention Cohort of Part 2	17
1.3.2. Part 2 Treatment Cohort and Part 3	24
2. Introduction	28
2.1. Study Rationale	28
2.2. Background	28
2.3. Benefit/Risk Assessment	29
3. Objectives and Endpoints.....	31
4. Study Design	37
4.1. Overall Design	37
4.1.1. Screening Period	37

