4.3. Justification for Dose

Part 1

The 4200 mg single dose LY3819253 is selected for this study based on preliminary safety, tolerability, PK data from the first-in-human Study PYAA, and preclinical PK/PD modeling. Based on an estimated human half-life of approximately 19 days, a single dose of 4200 mg may be necessary to have a sustained lung concentration above the *in vitro* IC₉₀ of viral cell-entry neutralization in 100% of participants for 4 weeks and in 90% of participants for a minimum of 8 weeks.

Part 2 and Part 3

LY3819253

LY3819253 700 mg was estimated as the maximum therapeutic dose based on PK/PD viral dynamics modeling and observed data from Study PYAB and has a sustained concentration above the *in vitro* IC₉₀ of viral cell-entry neutralization in the lung tissue (95th percentile of the estimates used) for at least 28 days in 90% of the participant population. The lower dose of 350 mg was selected to evaluate the lower limit of the confidence interval for clinical IC₉₀, based on emerging data from ongoing study. At dose levels greater than 700 mg, LY3819253 provides exposure coverage in at least 90% of participant population for approximately 8 weeks.

LY3832479

The LY3832479 1400 mg dose was selected as the maximum therapeutic dose based on PK/PD viral dynamics modeling, relative IC₉₀ potency to LY3819253, and has a sustained concentration above the *in vitro* IC₉₀ of viral cell-entry neutralization in the lung tissue for at least 28 days in 90% of the participant population. The LY3832479 700 mg dose was selected to evaluate the lower limit of the confidence interval for clinical IC₉₀. On average, the 3 dose levels are expected to provide exposure coverage (as described in Part 1) for approximately 8 weeks. At dose levels greater than 700 mg, LY3832479 provides exposure coverage in at least 90% of participant population for at least 8 weeks.

LY3819253 + LY3832479 Combination

To provide coverage of the different but overlapping epitopes on SARS-CoV-2 receptor binding domain sites, the dose selection rationale for each single mAb intervention in the combination is the same as for the individual dose rationale for a single mAb intervention described above.

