5.2. Exclusion Criteria

Participants are excluded from the study if any of the following criteria apply:

7. For Parts 1 and 2, recovered from COVID-19 disease or asymptomatic infection
8. For Parts 1 and 2, a prior history of a positive SARS-CoV-2 serology test
9. For Parts 1 and 2, a history of Convalescent COVID-19 plasma treatment
10. Are an inpatient in hospital
11. For Parts 1 and 2, participation in a previous SARS-CoV-2 vaccine trial or received an approved SARS-CoV-2 vaccine
12. For Parts 1 and 2, previous receipt of SAR-CoV-2-specific monoclonal antibodies
13. Have participated, within the last 30 days, in a clinical study involving an investigational product. If the previous investigational product has a long half-life, 5 half-lives or 30 days (whichever is longer) should have passed. This criterion does not apply to products described in Criteria 9, 11, and 12.
14. Are pregnant or breast feeding
15. Are concurrently enrolled in any other type of medical research judged not to be scientifically or medically compatible with this study
16. Have known allergies to related compounds of LY3819253, LY3832479 or any components of the formulation
17. Suspected or proven serious, active bacterial, fungal, viral, or other infection that in the opinion of the investigator could constitute a risk when taking investigational product
18. Have any serious concomitant systemic disease, condition or disorder that, in the opinion of the investigator, should preclude participation in this study.

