6.5. Concomitant Therapy

Concomitant Therapy

Participants should be treated according to standard of care, even as it evolves, and medications may be part of the treatment paradigm.

Remdesivir may be initiated as standard of care for participants requiring hospitalization.

If the local standard of care per written policies or guidelines (that is, not just an individual clinician decision) includes investigational agents to treat COVID-19, then starting these during the study is permitted, but may require additional safety monitoring.

Convalescent COVID-19 plasma treatment is not allowed, except in hospitalized participants.

Vaccines for SARS-CoV-2 should not be used prior to Week 8 of the evaluation period for the prevention cohort of Part 2.

Any medication, investigational agent, or vaccine, including over the counter or prescription medicines, vitamins, and/or herbal supplements, or other specific categories of interest (such as convalescent COVID-19 plasma treatment) that the participant is receiving at the time of enrollment or receives during the study must be recorded along with

- Reason for use
- Dates of administration including start and end dates, and
- Dosage information including dose and frequency for concomitant therapy of special interest.

Acetaminophen and corticosteroid use are permitted at any time during the study.

Other concomitant medication may be considered on a case-by-case basis by the investigator in consultation with the sponsor if required.

The sponsor should be contacted if there are any questions regarding concomitant or prior therapy.

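### Part 3 admits people with earlier SARS-CoV-2 antibody or convalescent plasma in order to explore safety in them, but its schedule does not systematically record either exposure

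*Protocol*

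**What the plan says.** **Purpose.** The rationale for the current protocol amendment says Part 3 may enrol people with COVID-19 who recovered from an earlier infection, or who previously had convalescent plasma, a monoclonal antibody or a vaccine. On the reason it states: "Inclusion will allow for collection of data to explore safety of treatment of LY3819253 alone or in combination with LY3832479" in any of these groups.

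**Eligibility (Protocol 5.2).** Criterion 9 now reads "For Parts 1 and 2, a history of Convalescent COVID-19 plasma treatment", and criterion 12 (prior SARS-CoV-2-specific antibody) is limited to Parts 1 and 2 in the same way. Criterion 13 sets a washout of 30 days or 5 half-lives after an investigational product, then adds: "This criterion does not apply to products described in Criteria 9, 11, and 12". Part 3 therefore admits prior antibody and plasma recipients at any interval.

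**Capture (Protocol 1.3.2).** The row for prior treatments of special interest reads: "Within the last 2 weeks: NSAIDs, antivirals, antibiotics, anti-malarials, corticosteroids, immunomodulators, or other investigational treatments. At any time: SARS-CoV-2 vaccine".

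**Concomitant therapy (Protocol 6.5).** The recording duty covers therapy "that the participant is receiving at the time of enrollment or receives during the study must be recorded".

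**Drug concentration (Protocol 1.3.2).** For the Part 3 PK sample the comment is "Day 1: post-dose only (approx. 30 minutes after end of infusion"). In Part 1, which excludes these people, the Day 1 PK sample is pre-dose (Protocol 1.3.1).

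**Stratification (Protocol 6.3).** Prior vaccine is the only prior exposure used as a stratification factor in Part 3.

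**The concern.** The amendment newly admits three product exposures to Part 3: plasma, antibody and vaccine. The prior-treatment row was lengthened for vaccine alone. A site that follows the schedule exactly has no instruction to record an antibody infusion or a plasma transfusion completed three weeks or three months earlier. Even inside 2 weeks, either product would have to be read into the entries for immunomodulators or investigational treatments, and a site may not class an authorised antibody as investigational.

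Two things are at stake. First, safety after prior antibody or plasma cannot be summarised reliably if membership of those groups depends on what each site happens to write down, and the history may be hard to recover after screening. Second, a Part 3 participant who still carries LY3819253 or LY3832479 has higher concentrations than the assigned dose explains, and the scheduled samples do not show why.

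**Working it through.** The documents give no figure to reproduce: Part 3 is exploratory, has no power calculation, and no number is stated for prior antibody or plasma recipients. The check compares the texts and adds one illustration.

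**1. Can another stated route capture the exposure?**

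- *Concomitant therapy (Protocol 6.5):* covers therapy at enrolment or later. A completed past dose is neither.
- *Medical history (Protocol 1.3.2, 8.2.1):* has no time limit, so it could pick the exposure up, but nothing prompts for product, dose or date. SAP Table PYAD.6.5 tabulates it as MedDRA-coded conditions.
- *Prior medications (SAP 6.9):* defined without a 2-week limit, but the table can show only what was collected.
- *Day 1 serology (Protocol 1.3.2):* drawn pre-dose. The assay target is not given, and nothing says the assay can tell infection, vaccine, plasma and monoclonal antibody apart.
- *Extra PK samples (Protocol 8.5):* up to 3, at discretion, so not systematic.

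None of these requires that prior antibody or plasma be identified.

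**2. How much LY3819253 could remain past the look-back?**

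Input: "Based on an estimated human half-life of approximately 19 days" (Protocol 4.3). Assumptions: first-order decline, and the earlier product was LY3819253. Half-lives of 15 and 25 days are an assumed range.

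Residual fraction = 0.5^(days / half-life)

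| Days since earlier dose | Half-life 15 d | 19 d | 25 d |
|---|---|---|---|
| 14 | 52% | 60% | 68% |
| 15 | 50% | 58% | 66% |
| 30 | 25% | 33% | 44% |
| 60 | 6% | 11% | 19% |

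Five half-lives, the interval named in criterion 13, is 5 × 19 = 95 days. A 14-day look-back covers 14/95 = 15% of it.

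**3. What would the PK samples show?**

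Suppose the earlier dose was 700 mg, 15 days before. Body load after a 700 mg study dose is 700 + 0.579 × 700 = 1105 mg, or 1.58 times the assigned dose. Under the same first-order decline both portions fall in parallel, so the ratio is unchanged at Days 29 and 85. Later samples cannot separate them either.

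**4. What share would be missed?**

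If earlier dosing were spread evenly over the last W days, the share outside the look-back is 1 − 14/W: 33% for W = 21, 50% for 28, 77% for 60 and 85% for 95. The documents give no W.

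**The case against.** The other side has several fair points.

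- *Size.* A reader might infer that most prior recipients are unidentifiable. The documents do not support that. They give no timing, and under even spacing a majority is missed only if W exceeds 28 days. Medical history may catch some, and the CRF is not among the documents. What the text supports is that capture is not systematic.
- *Measurement.* A reader might infer that residual antibody goes unmeasured. Pre-dose serology, antidrug antibody and biomarker samples are all taken on Day 1, and serology-positive people are left out of the Part 3 Treatment population. Only a pre-dose drug concentration is unscheduled.
- *Same drug.* A reader might infer that Part 3 re-doses people with the study antibody. The amendment covers any SARS-CoV-2 antibody, and plasma. The documents give no half-life for LY3832479, other antibodies or plasma.
- *Timing.* The Part 3 schedule requires the first positive sample within 10 days before infusion, so antibody or plasma given after that test falls within 2 weeks. The gap past 2 weeks concerns prophylaxis or an earlier infection, and the documents do not say how common either is.
- *Harm.* The 1105 mg in the example is well below the 4200 mg given in Part 1, so the 1.58 ratio is no sign of a dose-related hazard. It bears on reading the concentrations.
- *Intent.* The amendment rationale promises no subgroup analysis, and Protocol 4.2 names only vaccine recipients when it explains the change. SAP Version 4 was written for amendment (c), so its silence on the present amendment is a version lag.

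These points limit the size of the problem. They do not answer the mismatch: the rationale names prior antibody and plasma recipients among the groups to be explored, and no stated rule requires a site to identify them.

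**Conclusion.** The point holds in this form: Part 3 admits prior antibody and plasma recipients at any interval in order to explore safety in them, but the schedule neither names these products nor looks back more than 2 weeks for them. Because Day 1 PK is post-dose only, any carried-over LY3819253 or LY3832479 cannot be told apart from the study dose.

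The number affected is unknown. The illustrative residual for LY3819253, 58% at 15 days and 33% at 30 days (50% to 66% and 25% to 44% over half-lives of 15 to 25 days), rests on first-order decline and on the earlier product being that antibody. It shows that the exposure can outlast the look-back by a wide margin, not that it commonly does.

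Part 3 is exploratory and no confirmatory test depends on this. It should still be corrected, because the amendment's own aim depends on knowing who was exposed.

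**What to change.** 1. **Protocol 1.3.2, comment on prior treatments.** Extend the any-time list to three items: SARS-CoV-2 vaccine; SARS-CoV-2-specific monoclonal antibody, with product, dose and date; and convalescent plasma, with date.
2. **Next SAP version.** Summarise Part 3 safety descriptively by prior-antibody and prior-plasma status. Show Part 3 concentrations of prior-antibody recipients apart from the main summary. Table PYAD.6.1 lists only Part 1 and Part 2 groups for the pharmacokinetic population, so the Part 3 groups need adding there.

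**Cost.** A few CRF fields at screening, some site effort to obtain the history, and a short SAP addition. No new visit or sample is needed, and no eligibility or dosing rule changes.

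**What it leaves open.** The history identifies exposed participants but does not measure their residual drug level, which would take a pre-dose concentration. Histories given from memory or through a representative may also be incomplete. With 30 to about 500 participants in Part 3, the exposed groups may be small and should be read descriptively.
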